6.2 Safety Endpoints

All safety analyses will be performed on the SES. All safety tables will be presented by actual treatment group (“Group P”, “Group U”, “Group G&H”) at V2 in MP. In TEAE tables for total OLEX period, Cycle 2, and Cycle 3, the column headers for these three treatment groups will be “MP Group P”, “MP Group U”, “MP Group G&H”. TEAE tables for MP will additionally include a “Total NT 201” column for which active treatment groups (Group U and Group G&H) will be pooled. TEAE tables for total OLEX period, Cycle 2, and Cycle 3 will present pooled results from all three treatment groups in the fourth column, which will be labeled “Total”. For TEAE analyses over total study period, the columns “MP Group P - MP”, “MP Group P - OLEX”, “MP Group U”, “MP Group G&H” and “MP Total NT 201” (“MP Group P – OLEX, MP”, “Group U” and “Group G&H” pooled) will be presented. In column “MP Group P - MP” only AEs which occurred during MP are counted, in column “MP Group P - OLEX” only AEs which occurred in OLEX period are counted.

All analyses of laboratory values from any timepoint (Screening V1 and end-of-study visit V17) will be performed by actual treatment group at V2 in MP and in total. All analyses of vital signs from any timepoint will be performed by actual treatment group at V2 in MP, Total NT 201 (labeled “MP Total NT 201” for analysis of vital signs from visits total OLEX period) and in total.

AEs will be coded according to the MedDRA version in effect at the time the database is closed. Only TEAEs will be analyzed, which are defined as AEs with onset or worsening on or after date of the first administration of investigational product (IP) up to and including end of study visit (V17). In case no end of study visit (V17) is performed, all AEs reported during a time period corresponding to the expected cycle length will be regarded as treatment-emergent. Further details for separation of TEAEs and non-TEAEs can be found in CC1. Non-TEAEs will be listed only.

All analyses of TEAEs will be based on the following time periods:

- Total study period
- MP (Cycle 1)
- Total OLEX period (Cycle 2 and Cycle 3)
- Cycle 2
- Cycle 3.

TEAEs of the MP are defined as AEs with onset or worsening on or after date and time of the first administration of IP at V2 and before date and time of administration of IP in V8 (Cycle 2) or up to and including end of study visit (V17) in case of premature discontinuations prior to V8. For subjects who do not receive study treatment during OLEX period all AEs with onset or worsening on or after date and time of the first administration of IP up to and including end of study visit (V17) will be considered as TEAEs of MP. In case no end of study visit (V17) performed, all AEs with onset or worsening up to and including Day 120 of MP will be regarded as TEAEs of MP.

TEAEs of the total OLEX period are defined as AEs with onset or worsening on or after date and time of the first administration of IP during OLEX period at V8 and up to and end of study visit (V17) visit. In case no end of study visit (V17) is performed, all AEs with onset or worsening at or after date and time of the first administration of IP during OLEX period at V8 and up to and including Day 120 of last cycle will be regarded as TEAEs of OLEX. TEAEs of Cycle 2 are defined as AEs with onset or worsening on or after date and time of the first administration of IP at V8 and before date and time of administration of IP at V13 (Cycle 3) or up to and including end of study visit (V17) in case of premature discontinuations prior to V13 or in case no study treatment is

administered at V13. In case no end of study visit (V17) is performed, all AEs with onset or worsening at or after date and time of the first administration of IP at V8 and up to and including Day 120 of Cycle 2 will be regarded as TEAEs of Cycle 2. TEAEs of Cycle 3 are defined as AEs with onset or worsening on or after date and time of the first administration of IP at V13 and up to and including end of study visit (V17). In case no end of study visit (V17) is performed, all AEs with onset or worsening at or after date and time of the first administration of IP at V13 and up to and including Day 120 of Cycle 3 will be regarded as TEAEs of Cycle 3.

For analysis over the total study period, the number of subjects in the SES will serve as the denominator for calculation of incidences. For the analyses by treatment cycle the denominator will be adjusted to all subjects being treated in that treatment cycle. For the analysis over the total OLEX period, the denominator for the incidences will be all subjects being treated at least once in total OLEX period.

If an AE worsens between start and end of this AE it will be considered as new AE starting with the date of worsening. In this case the imputation of end dates within episodes of the same AE will be done by setting the end date/end time to start date/start time of the consecutive worsening record.

For analysis, incompletely recorded or completely missing start of AEs will be estimated according rules laid down in **CCI**. End dates will not be imputed. In the AE listing, start date as recorded and as imputed for analysis will be displayed.

Calculation of time to onset/duration of AEs (days):

- Time to onset of an AE is defined as start date of AE - date of first administration of study drug in respective treatment cycle [+ 1 day for TEAEs]
- The duration of an AE will be calculated as stop date - onset date + 1 day.

If a subject has more than one intensity/ causal relationship to treatment/ outcome within a preferred term (PT) only the worst intensity/ causal relationship to treatment/ outcome will be considered for calculation of incidence rates in the frequency tables reporting incidences by intensity/ causal relationship to treatment/ outcome. Incidence of TEAEs related to COVID-19 disease and TEAEs related to COVID-19 vaccination will only be calculated overall. Thereby, TEAEs with missing relationship will be ignored but affected subjects will not be removed from the denominator. Also, for the analysis overall, i.e. for subjects with at least one TEAE, only the worst intensity/ causal relationship to treatment/ outcome category per subject will be counted for calculating incidence rates. The same applies to calculation of overall incidence of TEAEs related to COVID-19 disease and TEAEs related to COVID-19 vaccination.

The worst outcome is defined in the following order (worst outcome to best outcome):

- fatal
- unknown
- not recovered/not resolved
- recovering/resolving
- recovered/resolved with sequelae
- recovered/resolved

AEs coded as “Immunisation reaction” (preferred term) are defined as AEs related to COVID-19 vaccination.

The AEs listed in **CCI** are defined as adverse event of special interest (AESIs) for this study.

CCI

In case of missing intensity or missing causal relationship of an AE to treatment, the worst case principle will be applied, i.e., a missing intensity will be set to “severe” and a missing causal relationship will be set to “related”. Missing outcome will be set to “unknown”. Missing causal relationship to COVID-19 disease will not be imputed. TEAEs with missing relationship to COVID-19 disease will be ignored for calculation of the respective incidence rates but affected subjects will be kept in the denominator and only TEAEs which are documented as related to COVID-19 disease will be included in respective listing. No missingness is expected for relationship of TEAEs to COVID-19 vaccination.

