6.2 Discussion of study design, including choice of control groups

The prospective, randomized, double-blind, placebo-controlled, multicenter design of the MP of this Phase 3 study was chosen to investigate the efficacy and safety of simultaneous treatment of UFL with NT 201 with minimized risk of bias by including a placebo control. Robust results are expected from the study design.

CCI

CONFIDENTIAL

CCI

CCI

The observation period of 120 days (4 months) (plus 30 days if subjects have not yet relapsed to enter the OLEX period) between first injection and reinjection, represents a reasonable time that the IP will have worn off in most of the treated subjects, so that reinjection in the OLEX period can be performed safely.

CCI

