8.2 Treatments administered

In the MP (Cycle 1) subjects will be randomized to one of three treatment groups CCI

- In Group U, subjects will receive 20 U NT 201 in the GFL area, 20 U NT 201 in the HFL area, and 24 U NT 201 in the LCL area (12 U per side).
- In the G&H group, subjects will receive 20 U NT 201 in the GFL area, 20 U NT 201 in the HFL area, and placebo in the LCL area.

- In the P group, all three areas will be treated with placebo.

In the OLEX period (Cycles 2 and 3), all subjects will receive NT 201 in all three areas

CCI

Injections will be administered as described in [Section 8.1.1.2](#).

CCI

In case of a public health emergency further treatments may be halted or postponed.

8.2.1 **Methods of assigning subjects to treatment groups**

At baseline visit V2, subjects will be randomized 2:1:1 to one of the three treatment groups (Groups U, G&H, or P). Randomization will be done by using an IWRS. Randomization numbers and date of randomization will be recorded in the eCRF.

Randomization will be stratified by investigational site and will be in blocks of appropriate size. This will ensure an approximately equal ratio of treatment groups between sites. The block size will not be disclosed to investigators until the study is unblinded.

No other criteria for stratification of randomization will be applied.

If subjects are discontinued from the study during the MP, no replacement of subjects is planned.

8.2.2 ***Selection of doses in the study***

The choice of the doses per treatment area used in this study are justified by experience from prior studies performed with NT 201 ^{CCI}

^{CCI}

^{CCI} as well as by published results from clinical studies with other BoNTA- preparations.

^{CCI}

A placebo-controlled study with total doses of 64 U of BoNTA- injected in a comparable manner as planned in this study showed that this dose is safe and effective for the treatment of UFL [De Boulle 2018].

[figure not shown]
The doses chosen in this study are also in accordance with the treatment doses recommended in the labeling for ^{CCI}

^{CCI}

8.2.3 ***Selection and timing of doses for each subject***

In the MP (Cycle 1), subjects will be randomized to one of the three treatment groups as described in Section 8.2 ^{CCI} Treatment (NT 201 or placebo) will be administered at the baseline visit V2 according to the instructions detailed in Section 8.1.1.2 and the ^{CCI} in ^{CCI}

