After a 120 day observation period following injections in cycles 1 and 2, eligible subjects will receive NT 201 reinjection ^{CCI} at the next cycle baseline visit (V8 for Cycle 2 and V13 for Cycle 3) according to the instructions detailed in Section 8.1.1.2 and the injection scheme shown in ^{CCI}. The end-of-Cycle 1 visit V7 and the Cycle 2 baseline visit V8, as well as the end-ofCycle- 2 visit V12 and the Cycle 3 baseline visit V13 should be on the same day if eligibility criteria are fulfilled at V7 and V12.

8.2.4 ***Duration of treatment per subject***

Subjects will receive study medication at up to three injection visits.

The overall study duration will be approximately 360 days plus the individual duration of screening until baseline (up to 14 days) plus a maximum of 30 days after Cycle 1 and Cycle 2, respectively, for eligibility reassessment, as applicable.

In case of a public health emergency the study might be halted, recruitment interrupted, and/or study processes and flow might be modified with impact to the study duration/visit schedule depending on the current study status. This might include, but is not limited to, extending study visit windows, performing study visits by phone or video, and/or performing efficacy assessments remotely

8.2.5 ***Treatment compliance***

The IP(s) will be administered to the three facial areas by intramuscular injection performed by the investigator during the subject's visits at the site at study baseline (V2) and at cycle baselines in the OLEX period (V8 for Cycle 2 and V13 for Cycle 3). Thus, full treatment compliance is assured for each individual subject.

8.2.6 ***Treatment of overdose***

An overdose is defined as any deviation from the specified dose in the protocol (doses that are higher than recommended). Any overdose must be recorded in the IP section and the AE section of the eCRF and the source documents. Any case of overdose leading to serious adverse events (SAEs) or AEs of special interests (AESI) must be reported to the CRO in an expedited manner using the appropriate reporting form (Section 10.1).

As treatment with IP is performed exclusively in a clinical setting under the supervision of trained medical personnel, the risk of overdose in this study is estimated to be very low. For the IP used in this study, no antidote has been identified to date, and there is no known therapy recommended for an overdose.

CCI

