possible within 30 days after V7 (Section 8.2.3). After treatment in Cycle 2, subjects will be followed up during four control visits (V9 to V12) for 120 days. Control visit V12 is also the end-of Cycle- 2 visit.

After completion of Cycle 2, eligible subjects will continue in Cycle 3, where they will receive treatment with NT 201 for all three facial areas at the Cycle 3 baseline visit V13. The end-of-Cycle 2 visit V12 and the Cycle 3 baseline reinjection visit V13 can be performed on the same day if all required eligibility criteria and none of the exclusion criteria of the OLEX period (Section 7.3) are met at V12. Reassessment for eligibility is possible within 30 days after V12 (Section 8.2.3). After treatment in Cycle 3, subjects will be followed up during four control visits (V14 to V17) for 120 days. Control visit V17 is also the end-of Cycle 3 and -end-of study- visit.

The study activities and visit schedules are shown in CCI for the MP and in CCI for the OLEX period. The clinical study protocol allows for a window of ± 7 days in scheduling of study visits for all post-baseline visits, except V3 where only a ± 3 -day window is allowed. The IP(s) must be injected by the investigator, who is trained and experienced in aesthetic BoNT treatment, at the study site. Following administration of IP(s), subjects will be observed for a minimum of 30 minutes at the site and will be asked by the investigator if any AEs have occurred since administration. Vital signs will be taken at the beginning of each study visit to ensure subject safety.

The last primary outcome visit will occur at Day 30 ± 7 (V4) for each subject. For subjects not fulfilling the reinjection criteria, also not at the reassessment visit, the end-of study visit will be performed directly and the subject will be discontinued from the study. For all other subjects, the -end-of study- visit V17 will occur at Day 120 ± 7 after last administration of the IP in Cycle 3. Unscheduled visits may be required in the case of AEs or premature discontinuation of the study. In this case, the final assessments as described for V17, will be performed as soon as possible. If additional safety follow-up is necessary after this visit, subjects may be contacted by telephone or be assessed in the clinic, depending on the nature of the follow-up required.

CCI

CCI

CCI

CCI

[figure not shown]
CCI

CCI

CCI

CCI

CCI

CCI

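### Does letting the main-period TEAE window run to the next injection bias the comparison of NT 201 with placebo?

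*SAP*

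**What the plan says.** SAP Section 6.2 (Safety Endpoints) starts the MP window at the V2 injection. It closes "before date and time of administration of IP in V8 (Cycle 2) or up to and including end of study visit (V17"); the second limb is for premature discontinuation before V8. Subjects never treated in the open-label extension (OLEX) are also counted up to V17. The only fixed limit is for a missing final visit: "In case no end of study visit (V17) performed, all AEs with onset or worsening up to and including Day 120 of MP" are then counted. Cycle 2 follows the same pattern, with V13 in place of V8. MP incidences use all subjects treated in the cycle as denominator, and the MP tables set Group P beside Group U, Group G&H and the two active groups pooled.

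The Protocol determines when V8 happens. Under Section 8.2.3, V7 and V8 "should be on the same day if eligibility criteria are fulfilled at V7 and V12". Otherwise Section 9.2 allows reassessment within 30 days after V7. Section 6.2 describes the interval as 120 days, "plus 30 days if subjects have not yet relapsed to enter the OLEX period", and says this "represents a reasonable time that the IP will have worn off in most of the treated subjects". Section 9.2 adds: "For subjects not fulfilling the reinjection criteria, also not at the reassessment visit, the end-of study visit will be performed directly". Treatment may also be delayed for reasons unrelated to arm: "In case of a public health emergency further treatments may be halted or postponed" (Section 8.2).

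**The concern.** The length of the window depends on something that happens after randomisation. A subject whose lines have returned by V7 is reinjected that day and contributes about 120 days. A subject whose effect persists can contribute about 150 days, 25% more. Placebo subjects have no active treatment to wear off, so the longer windows would be expected mainly on NT 201. With a crude numerator and a denominator of treated subjects, the longer-observed arm collects more events even if the drug causes none.

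The MP is the only placebo-controlled safety comparison in the trial, and related TEAEs in the MP are a named secondary safety endpoint (SAP Section 5.2.2). If the effect were large, part of an apparent NT 201 excess would come from longer observation.

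**Working it through.** **Plan figures.** The documents give no TEAE rate and no share of subjects expected to be delayed, so there is no plan figure on this point to reproduce. The related completion figure does reproduce: 180 × 0.85 = 153, which agrees with more than 150 Group U completers (SAP Section 3).

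**Inputs from the documents.** Nominal window 120 days; extension up to 30 days; Group U 180, Group P 90; about 15% not completing the MP.

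**Assumptions.** I = incidence by Day 120 without the extension; f = share of NT 201 subjects with a longer window; d = extra days; no true difference between arms; no delay on placebo. The last is the least favourable case for the plan.

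**All-cause TEAEs, constant hazard.** Excess = f × {1 − (1 − I)^((120+d)/120) − I}.

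- Smallest (I = 0.10, f = 0.10, d = 15): 0.10 × (0.1118 − 0.10) = 0.12 points.
- Middle (I = 0.20, f = 0.25, d = 30): 0.25 × (0.2434 − 0.20) = 1.09 points; with d = 15, 0.55 points.
- Largest (I = 0.20, f = 0.40, d = 30): 0.40 × 0.0434 = 1.74 points.

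**Related TEAEs.** Suppose most onsets fall soon after injection and only a share s = 0.10 to 0.25 of the Day 120 cumulative hazard H = −ln(1 − I) is spread evenly. Excess = f × {1 − exp(−H(1 + s·d/120)) − I}. With I = 0.20, H = 0.2231:

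- f = 0.25: 0.06 points (s = 0.10, d = 15) to 0.28 points (s = 0.25, d = 30).
- f from 0.10 to 0.40: 0.02 to 0.44 points. The maximum is 0.0044 × 180 = 0.8 of one subject.

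**Yardstick.** SE of the U-P difference = √{I(1 − I)(1/180 + 1/90)} = 3.9 points at 10% and 5.2 at 20%. The largest all-cause shift above is 1.74/5.2, about a third of an SE; the largest related shift is 0.44/5.2, under a tenth.

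**Wider all-cause range.** With I = 0.40, f = 0.50 and d = 30, the excess is 3.6 points against an SE of 6.3. The shift passes one SE only if every NT 201 subject is delayed the full 30 days and I is 30% or more (6.0 against 5.9 points at 30%; 7.2 against 6.3 at 40%). The Protocol expects wear-off in most treated subjects, so f near 1 is not what it anticipates.

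**What the model leaves out.**

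1. *Delay on placebo.* The excess scales with the difference in delayed shares. At I = 0.20 and d = 30, 25% on NT 201 against 10% on placebo gives 0.15 × 4.34 = 0.65 points instead of 1.09. Equal shares give zero.
2. *Early leavers.* For someone who leaves early and has a V17, that visit closes the window before Day 120. As an illustration, suppose V17 falls on Day 60 and I = 0.20. Expected incidence is then 1 − 0.8^0.5 = 0.1056, a loss of 0.0944 per such subject. A 5-point difference between arms in early leaving moves the comparison by 0.05 × 9.44 = 0.47 points, up or down depending on the arm. With about 15% non-completion assumed, this is of the same order as the effect in question.

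**Would a common cut help?** A plain Day 120 cut would be wrong. The ±7-day window allows V7 and V8 on about Day 113, so events after open-label NT 201 could enter the placebo column. Cutting at the earlier of Day 120 and V8 avoids that. If every eligible subject were reinjected on Day 113, it would still leave 0.06 to 0.42 points, against 0.12 to 1.76 without it. Incidence per subject-time errs the other way for early-clustered related events: at I = 0.20 and f = 0.25, the NT 201/placebo rate ratio is about 0.95 to 0.98 with no true difference.

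**The case for a change.** The strongest case for acting is that the mechanism is real and plausibly lopsided, and the remedy is cheap. The window rule is stated plainly, the extra time is tied to a persisting effect, the readable text has neither a common cut nor an exposure adjustment, and time to onset from the cycle's injection is already defined. One supplementary summary, with later events in their own row, would let a reader separate longer observation from a drug effect without altering any existing table.

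The first part stands: windows do differ in length between subjects, and more delay on NT 201 is a reasonable expectation. But it remains an expectation, because the reinjection criteria are redacted and delay can arise in any arm. The claim that something is missing is also weak. Much of the SAP's safety text is redacted, including Section 6.2.3, so a time-based display may already exist. The AE listing shows start dates, so late MP events can be identified in any case.

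What does not stand is the gain. The readable plan attaches no test or confidence interval to TEAE incidences, so no decision depends on the comparison. The extra summary would give a second figure for the same secondary endpoint, differing by less than one subject in Group U under the assumptions above.

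**Conclusion.** No change is needed. Running each cycle to the next injection is a fair trade-off: every event is assigned once, to the injection that preceded it, and nothing is lost while a subject awaits reassessment. The price is unequal observation time, worth 0.12 to 1.74 points on all-cause MP incidence under the main assumptions (10-20% by Day 120, 10-40% of NT 201 subjects delayed by 15-30 days, none on placebo). That is below one standard error throughout. For related TEAEs it is 0.02 to 0.44 points from 20%, provided most onsets are early.

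These figures assume no placebo delay and ignore the shorter windows of early leavers, so the net size and sign are not established. The delay effect by itself would overstate events on NT 201, which is the cautious direction for safety. Anyone reading a small all-cause excess in the MP tables should bear the unequal windows in mind; no stated result or conclusion depends on it.

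### Without a final visit, four of the five TEAE periods stop at Day 120, so a late event can drop out of their tables because it prevented that visit

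*SAP*

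**What the plan says.** SAP 6.2 reports TEAEs for five periods: total study, main period (MP), total OLEX, Cycle 2 and Cycle 3.

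If a subject is not reinjected and V17 is performed, events count from the injection through V17, whatever the day. The MP sentence begins "For subjects who do not receive study treatment during OLEX period all AEs with onset or worsening on or after date and time"; its window opens at the initial injection and runs through V17.

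If V17 is not performed, four of the five periods end on a fixed day:

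- Main period: "In case no end of study visit (V17) performed, all AEs with onset or worsening up to and including Day 120 of MP will be" classed as belonging to that period.
- Total OLEX: "up to and including Day 120 of last cycle will be regarded as TEAEs of OLEX".
- Cycle 2: "up to and including Day 120 of Cycle 2 will be regarded as TEAEs of Cycle 2".
- Cycle 3: "up to and including Day 120 of Cycle 3 will be regarded as TEAEs of Cycle 3".

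The total study period has no day number of its own. It falls under the general rule in SAP 6.2 and Protocol 10.1, which uses the expected length of a cycle without giving it in days. Only TEAEs are analyzed, and "Non-TEAEs will be listed only".

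Protocol 9.2 allows 7 days either side for every post-baseline visit except V3. It then adds a reassessment period: "Reassessment for eligibility is possible within 30 days after V12", with the same 30 days after V7.

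**The concern.** For a subject who is not reinjected, the same recorded event on, say, Day 125 is a TEAE if V17 later takes place and is not one if it never does. The protocol schedules contacts after Day 120, so events with later onset can be expected in the database.

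Classification then depends on whether the subject came back, and the event can decide that. Death is the clear case. Loss to follow-up is another route to a missing V17, with no link to severity.

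The incidence of related TEAEs in the MP and in OLEX is the secondary safety endpoint (SAP 5.2.2), and the period definitions govern every other TEAE table as well. The rule also runs against the SAP's own caution: in the same section, a missing causality is set to related and a missing intensity to severe.

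**Working it through.** The plan states no figure for this gap. The check is visit-window arithmetic, followed by applying the rule to test cases.

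**Inputs**

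- Cut-off without V17: Day 120 of the relevant cycle (SAP 6.2).
- Nominal end-of-cycle visit: Day 120. Window: plus 7 days (Protocol 9.2).
- Reassessment: up to 30 days after V7 or V12, so after Cycles 1 and 2 only (Protocol 8.2.4 and 9.2).

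**Uncovered days, Cycles 1 and 2**

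- Latest V7 or V12: 120 + 7 = Day 127.
- Latest reassessment: 127 + 30 = Day 157.
- Gap: 157 − 120 = 37 days (Days 121 to 157), or 37/157 = 24% of the longest permitted cycle.
- If V7 or V12 falls on Day 120 itself: 120 + 30 = Day 150, a gap of 30 days.

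**Uncovered days, Cycle 3**

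- No reassessment follows. Latest V17: 120 + 7 = Day 127. Gap: 127 − 120 = 7 days (Days 121 to 127).

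**The rule applied to a subject in Cycle 1 or 2 who is not reinjected**

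| Onset day | V17 at Day 157 | V17 never performed |
|---|---|---|
| 119, 120 | TEAE | TEAE |
| 121, 125, 127, 135, 150, 157 | TEAE | not a TEAE for that period |

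**Total study period**

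- If the expected cycle length is 120 days, the same events are missing here too. SAP 2 gives the MP as 120 days plus screening, and Protocol 8.2.4 places the 30 days after Cycles 1 and 2, both of which favor this reading.
- SAP 2 also describes the OLEX cycles as 120 days with up to 30 more for reassessment. If that means 150 days for Cycle 2, an event on Days 121 to 150 would be in the total-study table but in neither the Cycle 2 nor the total OLEX table. Days 151 to 157 would still be uncovered.
- The general rule refers to events reported in the window, while the period rules refer to onset or worsening. The two could therefore classify one event differently.

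**Onset and worsening**

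- An event that began by Day 120 and later proved fatal keeps its original record in the tables.
- SAP 6.2 treats a worsening as a new event, so a worsening after Day 120 falls outside as a separate episode.

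**A side effect of the wording**

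- Read literally, the MP and Cycle 2 sentences could also apply to a subject who was reinjected after Day 120 and then missed the final V17. An event between Day 121 and the reinjection would drop out of that cycle's table, although it could remain in a table for a wider period.

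**The case against.** The strongest reply is that the rule will seldom apply. Protocol 7.4.1 requires an end-of-study visit after discontinuation. Protocol 9.2 sends subjects who fail the reinjection criteria, including at reassessment, directly to that visit. Their events count without a day limit. A fixed window for subjects without a final visit is also prespecified in principle in both documents, and Protocol 6.2 expects the product to have worn off in most subjects by 120 days, so related events that late should be uncommon. All of this stands. It limits the number of subjects affected, but it also means that those left without V17 will be mainly deaths and losses to follow-up.

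A reader might infer more than the documents support:

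- That such an event is missing from all TEAE tables. Day 120 is explicit for four periods only. SAP 6.2 also refers to an appendix on separating TEAEs from non-TEAEs that is blacked out in the public version and could add a rule.
- That 37 days are lost in every cycle. This holds for Cycles 1 and 2. In Cycle 3 the figure is 7.
- That any fatal or incapacitating event is lost. Incapacity may only delay V17, and a late V17 still captures the event. A fatal event that began by Day 120 keeps its record.
- That the event disappears. It is still listed, and Protocol 10.2 requires serious events to be reported whether related or not.

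A last-contact rule can also be criticized because it makes the window depend on follow-up and sets no upper limit. That is a fair reason to consider the end of the permitted visit and reassessment window as an alternative.

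**Conclusion.** The point holds in limited form, and the rule should be changed. In a subject with no V17 and no reinjection, a recorded event with onset or worsening on Days 121 to 157 (Cycles 1 and 2) or Days 121 to 127 (Cycle 3) is left out of the MP, total OLEX, Cycle 2 or Cycle 3 tables that apply, and is only listed. It is also left out of the total-study table if the expected cycle length means 120 days, which is the better-supported reading but not the only one.

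The expected number of subjects is small, and the documents give no basis for estimating it. What matters is the selectivity: a death from an event with onset in that window would be excluded because it prevented V17, while an identical onset in a subject who returned would be counted.

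This rests on two assumptions: that the visit and reassessment windows are used up to their permitted limits, and that the blacked-out appendix does not override the text of SAP 6.2.

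**What to change.** In SAP 6.2, for the case without V17, replace Day 120 with death or last documented contact. Every event recorded after an injection and before any next injection then counts for that cycle. If a bounded window is preferred, end it no earlier than the end of the permitted visit and reassessment window: Day 157 in Cycles 1 and 2, Day 127 in Cycle 3.

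Apply one rule, based on onset or worsening, to all five periods including the total study period. Either define the expected cycle length in days or remove the term, and align Protocol 10.1. Limiting the window to events before any next injection also settles the literal reading for subjects who were reinjected and later missed V17.

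The cost is a wording change and one derivation rule in the adverse event dataset. No new data are needed and no event counted now would be lost. The drawback is a window that varies slightly between subjects.
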